### **Sampling Technique**

Convenient sampling technique will be used to collect the selected sample size. Samples will be taken from all the patients with positive plasmodium vivax who fulfill the inclusion criteria.

### **Study Variables**

#### **Independent Variables**

- Age, Sex, Weight, Axillary temperature, leukocyte count, asexual and/ or sexual parasites count, Hemoglobin count

#### **Dependent Variables**

- Therapeutic Efficacy of CQ+PQ

### **Operational Definitions and Definition of Terms**

#### **Loss to Follow-Up**

Loss to follow-up occurs when, despite all reasonable efforts, an enrolled patient does not attend the scheduled visits and cannot be found. No treatment outcome will be assigned to these patients. Every effort must be made to schedule a follow-up visit for patients who fail to return to the study site, especially during but also after administration of the study drug. These patients will be classified as lost to follow-up and censored or excluded from the analysis. Patients who are lost to follow-up but who subsequently return to the study site before day 42 will not be turned away and will be encouraged to return for check-up visits. The principal investigator will decide whether the patient is to be classified as lost to follow-up based on his or her history or is to be maintained for the analysis.

#### **Patient Discontinuation or Protocol Violation**

Patients meeting any of the following criteria will be withdrawn:

- Withdrawal of consent
- Failure to complete the treatment
  - Vomiting both initial and replacement doses at any single time in the treatment (i.e. If the patient vomits both attempts to administer the morning dose that would

- require withdrawal; however, vomiting the initial morning dose but not the morning replacement dose would not require withdrawal), persistent vomiting
- Severe side-effects necessitating hospitalization
  - Progression to severe malaria
  - Failure to attend the scheduled visit during the first 3 days
  - Enrolment violation
    - Severe malaria on day 0
    - Erroneous inclusion of a patient outside of the inclusion/exclusion criteria
  - Voluntary protocol violation: Antimalarial (or antibiotics with antimalarial activity) treatment administered by a third party or self-medication with antimalarial (or antibiotics with antimalarial activity) assessed by asking participants or their caretaker at follow-up visits (Annex VI)
  - Involuntary protocol violation
    - Occurrence during the follow-up of concomitant disease that would interfere with a clear classification of the treatment outcome
    - Detection of a mono-infection with another malaria species during follow-up
    - Misclassification of a patient due to a laboratory error (parasitemia) leading to the administration of the rescue treatment

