## **Evaluation Criteria**

### **Efficacy and Safety Evaluation**

#### **Classification of Treatment Outcomes**

The primary outcome of this study will be to monitor the efficacy of AL for *P. falciparum* and CQ for *P. vivax* as a routine follow up study and develop baseline and complementary efficacy data for DHA-PPQ against *P. falciparum* and *P. vivax* malaria in Ethiopia.

The classification of treatment outcomes will be based on an assessment of the parasitological and clinical outcome of antimalarial treatment according to the latest guidelines from WHO. Accordingly, all *P. falciparum* and *P. vivax* patients will be classified as having an ETF, LCF, LPF, or ACPR (Annex I).

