## Statistical Analysis

Every data from recruited patients will be imported into the WHO Excel sheet (double entry) which is designed for analysis of therapeutic efficacy study data. Data will be also entered in to IBM SPSS (version-26) software to calculate descriptive statistics (mean, median, standard deviations, range). Independent sample t-test will be used to compare baseline temperature and parasitemia between children and adults; mean blood Hb level at D0, D14, D28 and D42 between patients with parasitemia  $\geq 10,000$  and  $< 10,000/\mu\text{l}$  blood. Non-parametric (median) test for independent sample will be used to compare D1 parasitemia between children and adults and paired sample t-test will be used to compare mean Hb level between D0 and D14, D0 and D28, D14 and D28, D0 and D42, D28 and D42. All comparisons will be performed at 95% CI and significance level of 0.05.

Kaplan Meier (K-M) survival analysis and per protocol (PP) analysis will be used for estimation of primary outcomes and PP analysis method will be used to analyze secondary outcomes. The K-M survival analysis method provides better approximation of cure rates as it incorporates probabilities for censored data (incomplete observations due to LFU and withdrawals) in to the analysis. The WHO excel sheet is especially designed for estimation of cure rate based on K-M survival estimator analysis method.

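### Severe malaria with parasitaemia is a withdrawal in one section and a treatment failure in Annex 4; no text says which governs the primary analyses, and a literal reading censors failures

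*Combined protocol and SAP*

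**What the plan says.** **Withdrawal.** The section Patient Discontinuation or Protocol Violation opens with "Patients meeting any of the following criteria will be withdrawn" and lists "Progression to severe malaria" among the criteria. The item carries no condition about parasitaemia and no exception for a patient who has already met a failure criterion.

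**Failure.** Annex 4 makes severe malaria with parasitaemia an early treatment failure on days 1 to 3 and a late clinical failure on days 4 to 42. Its second list, headed Treatment Failure (TF), counts clinical deterioration from *P. vivax* that needs hospital admission while parasites are present. Emergency Care admits patients with signs of severe malaria, so that criterion can be met as well.

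**Analysis.** Under Statistical Analysis, "Kaplan Meier (K-M) survival analysis and per protocol (PP) analysis will be used for estimation of primary outcomes". K-M is preferred there because it "incorporates probabilities for censored data (incomplete observations due to LFU and withdrawals". The PP set is not defined anywhere.

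**Text that bears on precedence.**
- Study Design classifies patients as failures or adequate responders and estimates efficacy from the proportion who fail during follow-up.
- Classification of Treatment Outcomes says that "all *P. falciparum* and *P. vivax* patients will be classified as having an ETF, LCF, LPF, or ACPR".
- Loss to Follow-Up states "No treatment outcome will be assigned to these patients", but only for patients who are lost.
- A garbled sentence in Rescue Treatment ties severe malaria criteria to treatment failure, in the context of second-line drugs.

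**The concern.** One event carries two labels, and the labels lead to different analyses. As an Annex 4 failure the patient is a K-M event. As a withdrawal the patient is, on the literal wording of Statistical Analysis, a censored observation. Censoring would then be caused by the outcome itself, which breaks the K-M assumption that censored patients have the same prospects as those still followed. The same choice arises in PP if withdrawn patients are left out.

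At stake is the main efficacy estimate of a single-arm, open-label study that expects few failures. The cases that could drop out are the most serious failures, and the person coding the record could enter either label and still be following the protocol.

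**Working it through.** **Plan's own figures.** Inputs from Sample Size Determination: expected failure 5%, margin 5 points, z = 1.96, 20% loss.
- n = 1.96² × 0.05 × 0.95 / 0.05² = 72.99, rounded up to 73.
- 73 × 1.2 = 87.6, rounded up to 88.

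Both stated figures reproduce, and neither depends on the disputed label. Expected failures are 0.05 × 73 = 3.65, taken as 4.

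**Assumption.** Let k be the number of those 4 failures that are severe malaria with parasitaemia. The documents give no rate, so k is assumed and may be 0.

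**Direction.** Whether a case is an event or is censored, the patient leaves the risk set on the same day and all later risk sets are identical. The only difference is that the event adds a factor below 1 to the survival product. In PP, (4 − k)/(73 − k) is below 4/73 for any k ≥ 1. So the withdrawal label can only lower the failure estimate.

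**K-M illustration.** Assumed: 88 enrolled; 15 losses, spread as 3, 3, 3, 2, 2, 2 after days 3, 7, 14, 21, 28, 35; severe cases on day 3; the other 4 − k failures on day 28. Eleven losses come before day 28, so 88 − 11 − k are at risk that day.

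| k | Counted as failure | Censored | Gap (points) |
|---|---|---|---|
| 0 | 4/77 = 5.19% | 5.19% | 0 |
| 1 | 1 − (87/88)(73/76) = 5.04% | 3/76 = 3.95% | 1.09 |
| 2 | 1 − (86/88)(73/75) = 4.88% | 2/75 = 2.67% | 2.21 |

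**PP illustration, if withdrawn patients are excluded** (exact 95% intervals in brackets).

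| k | Failure proportion | Gap from k = 0 (points) |
|---|---|---|
| 0 | 4/73 = 5.48% (1.5 to 13.4) | 0 |
| 1 | 3/72 = 4.17% (0.9 to 11.7) | 1.31 |
| 2 | 2/71 = 2.82% (0.3 to 9.8) | 2.66 |

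**Sensitivity.**
- Severe cases on days 1 to 3, other failures on day 21, 28 or 42: K-M gap 1.09 (k = 1) and 2.21 (k = 2).
- Severe cases as late as day 28: 1.09 to 1.30 (k = 1) and 2.21 to 2.60 (k = 2).
- Total failures varied from 2 to 6, k = 1: K-M gap 1.06 to 1.30, PP gap 1.27 to 1.35.

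This gives roughly 1.1 to 1.4 points per case.

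**The case against.** The strongest reply is that withdrawal and failure do not compete. The withdrawal section says when a patient leaves the study; it does not say that the patient then has no outcome. Only Loss to Follow-Up withholds an outcome, and only for lost patients. Study Design bases efficacy on failures during follow-up, and a patient with severe malaria and parasites on day 2 or day 10 has failed during follow-up. The K-M sentence explains a choice of method and speaks of incomplete observations; a patient who has met a failure criterion is complete. On this view the patient is classified first and then leaves.

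Most of this stands, and it is the better-supported reading. But it has to be inferred. The classification of all patients has no category for those who withdraw consent or violate the protocol, so its wording cannot settle precedence by itself.

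Three further points:
- The plan says "The WHO excel sheet is especially designed for estimation of cure rate based on K-M survival estimator analysis method", and that sheet may code failure separately from withdrawal. The documents do not describe its coding, and someone must still decide which label to enter.
- List indentation in the withdrawal section is broken in the extracted text. If the item belongs under failure to complete treatment, the overlap shrinks to the dosing period. That period still includes early-failure days.
- The plan sets no efficacy threshold or test for the failure rate in the sections concerned, so no stated decision is shown to change.

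A reader might infer that the plan deliberately removes severe malaria from the failures, or that the PP analysis contradicts Annex 4. The documents support neither: several sections lean towards failure, and for PP the set is undefined, not contradictory.

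**Conclusion.** Wrong as written, with low to moderate severity. Two stated rules give different results for the same event in the primary K-M analysis, and no sentence says which prevails. The text favours failure without making it a rule. The literal withdrawal route always moves the estimate towards higher efficacy.

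The size is illustrative: nothing if no such case occurs, otherwise about 1.1 to 1.4 percentage points per case against about 4 expected failures. For one or two cases this is inside the 5-point margin, and the PP intervals above overlap heavily. A reader might infer that the result could be seriously distorted. That would need most of the expected failures to be severe malaria, for which the documents give no basis.

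The figures rest on the assumed timing of losses and failures and, for PP, on withdrawn patients being excluded. The conflict covers only severe malaria with parasitaemia after day 0. Severe malaria on day 0 is separately an enrolment violation. Severe malaria without parasites and admission for side-effects alone are outside it.

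**What to change.** Reconcile the withdrawal section, Statistical Analysis and Annex 4 by an analysis rule only, leaving clinical withdrawal and care as they are. Suggested text:

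> A patient who meets an Annex 4 failure criterion at or before withdrawal, and before any protocol violation, is an event in K-M on that day and is kept in the PP numerator and denominator. This holds even if a violation occurs later. All other withdrawals are censored in K-M and excluded from PP. An apparent failure later shown to be a laboratory misclassification or an enrolment violation does not count as a failure. Withdrawal for vomiting doses alone is not a failure event.

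Two parts of this need explanation. An earlier violation includes "concomitant disease that would interfere with a clear classification of the treatment outcome", so such a patient is censored rather than counted. The vomiting sentence is needed because the screening form in Annex 1 lists vomiting everything as a danger sign, and Annex 4 treats danger signs with parasitaemia as failure; without it, an uncompleted treatment could become a failure, a bias in the other direction.

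Report the number withdrawn for severe malaria with and without parasitaemia.

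The cost is one paragraph. Annex 8 already calls for a smear on any unscheduled day, so patients seen at the facility need no new data; a patient admitted directly elsewhere may have no study smear. The downside is that the failure rate may look slightly less favourable.

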### Study Design

This Therapeutic Efficacy study is a prospective evaluation of clinical and parasitological responses to directly observed treatment for uncomplicated vivax malaria (51,52). People with uncomplicated plasmodium vivax malaria who meet the study inclusion criteria will be enrolled and treated on site with Chloroquine plus Primaquine for *p.vivax* infection and monitored up to 42 days.

The follow-up will consist of a fixed schedule of check-up visits and corresponding clinical and laboratory examinations. On the basis of the results of these assessments, the patients will be classified as having therapeutic failure (early or late) or an adequate response.

The proportion of patients experiencing therapeutic failure during the follow-up period will be used to estimate the efficacy of the study drugs. Molecular analyses will be used to distinguish between a true recrudescence due to treatment failure and episodes of reinfection as well as determine polymorphisms of known resistance markers. In addition, drug level testing may be conducted depending on the availability of resources. .

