#### **Any other day:**

- Clinical assessment — referral in case of severe malaria/danger signs

- Measurement of axillary temperature
- Blood sampling for blood smears and filter paper
- Hemoglobin/hematocrit if indicated clinically
- Alternative treatment in case of treatment failure

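### Patients who take another antimalarial are withdrawn and censored whatever the reason or slide result, so the Kaplan-Meier cure rate can be biased upward, and no planned analysis would show it.

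*Combined protocol and SAP*

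**What the plan says.** Under Patient Discontinuation or Protocol Violation the rule opens with "Patients meeting any of the following criteria will be withdrawn", and one of the listed criteria is a "Voluntary protocol violation: Antimalarial (or antibiotics with antimalarial activity) treatment administered by a third party or self-medication with antimalarial". Such use is found by asking the patient or caretaker at follow-up visits. The criterion does not ask why the drug was taken, and it does not depend on the slide.

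The Statistical Analysis section states that "Kaplan Meier (K-M) survival analysis and per protocol (PP) analysis will be used for estimation of primary outcomes". It prefers Kaplan-Meier because the method "incorporates probabilities for censored data (incomplete observations due to LFU and withdrawals) in to the analysis". The per-protocol population is not defined. No sensitivity analysis, worst case or bound is given for the primary outcome.

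Annex 4 defines failure by parasitaemia within set windows:
- late clinical failure: from day 4 to day 42, with fever or a history of fever;
- late parasitological failure: from day 7 to day 42, without fever;
- the separate *P. vivax* definition: from day 7 to day 28/42, whatever the clinical state.

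None of these exempts a patient who has taken another drug. Annex 8 takes a smear at every scheduled visit, and its entry for any other day also lists "Blood sampling for blood smears and filter paper".

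**The concern.** Kaplan-Meier handles withdrawals without bias only if a patient censored on a given day has the same later risk of failure as those who remain. A patient who takes an antimalarial because fever has returned does not fit that assumption, since the event may already have happened. Censoring removes that patient from the risk set and credits the rest of the follow-up with the average risk of the others.

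Two features make this matter here. First, few failures are expected, so a handful of misclassified patients moves the estimate visibly. Second, the per-protocol analysis would usually omit the same patients. Agreement between the two primary estimates would therefore say little about whether failures had been lost through this route.

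There is also a gap in classification. A self-treating patient whose slide is still positive meets an Annex 4 failure definition and a withdrawal criterion at the same contact. In an unblinded study the order of precedence should be fixed before results are seen.

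**Working it through.** **The plan's own figures.** From Sample Size Determination: p = 0.05, d = 0.05, z = 1.96.
- n = 1.96² × 0.05 × 0.95 / 0.05² = 72.99, rounded up to 73.
- 1.2 × 73 = 87.6, rounded up to 88. The planned allowance for incomplete patients is 88 − 73 = 15.
- Expected failures: 0.05 × 73 = 3.65, taken as 4.

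The stated 73 and 88 are reproduced.

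**Assumptions, not in the documents.** Of the 15 incomplete patients, k took another antimalarial for a true recurrence. The 4 observed failures fall on days 21, 28, 35 and 42. The k patients leave on days 21 to 35, and the other incomplete patients are spread over days 7 to 35. The day-42 Kaplan-Meier cure rate is the product of (1 − failures / at risk) over the failure days.

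**Worked case, k = 4.**
- Hidden failures censored: 82/83 × 78/79 × 73/74 × 69/70 = 0.949, a failure rate of 5.1%.
- Hidden failures counted on the day of leaving: 81/83 × 76/79 × 72/74 × 69/70 = 0.900, a failure rate of 10.0%.

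**Range of k.** The per-protocol columns assume that this population leaves out all 15 incomplete patients, unless the k are added back as failures.

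| k | K-M failure, censored | K-M failure, counted | Per protocol, omitted | Per protocol, counted |
|---|---|---|---|---|
| 0 | 5.2% | 5.2% | 4/73 = 5.5% | 5.5% |
| 1 | 5.2% | 6.4% | 5.5% | 5/74 = 6.8% |
| 2 | 5.2% | 7.7% | 5.5% | 6/75 = 8.0% |
| 3 | 5.2% | 8.8% | 5.5% | 7/76 = 9.2% |
| 4 | 5.1% | 10.0% | 5.5% | 8/77 = 10.4% |

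**Sensitivity to timing.** Two simulations with 2,000 runs per scenario and different assumed event times gave 5.1% to 5.3% with the hidden cases censored. Counting 1, 2, 3 or 4 of them gave 6.3-6.5%, 7.4-7.7%, 8.6-8.9% and 9.7-10.1%. Each hidden failure adds about 1.2 points. The censored estimate hardly moves with k, so the planned output cannot reveal the problem.

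**If only some were failing.** With k = 4 and half of them true failures, the per-protocol rate is (4 + 2)/77 = 7.8%. With k = 5, cure is 94.5% if 5% were failing (no shift from 69/73 = 94.5%), 93.3% at 25%, 91.7% at 50% and 88.5% at 100%.

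**Bound.** If all 15 incomplete patients are counted as failures, the rate is (4 + 15)/88 = 21.6%.

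**The case against.** The strongest reply is that the documents show neither how often outside drug use will occur nor why. Annex 7 lists common antibiotics, such as azithromycin and doxycycline, which may be taken for unrelated illness and would then add little or no bias. The plan also works against outside treatment: patients live within 5 km, care is free, transport is paid, missed visits are followed up at home, and patients are told to return on any day if symptoms recur. All of this stands. It makes hidden failures less likely, but it does not change how one would be analysed.

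A reader might infer that the plan directs parasitaemic self-treaters to be misclassified. It does not: Annex 4 has no exception for outside drugs, and Annex 9 allows rescue treatment on any day that failure criteria are met. The documents set no precedence, so this is an unresolved conflict.

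A reader might also take it as stated that the per-protocol analysis drops these patients. That is the usual meaning of the term, but the plan never defines the population.

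On size, the 15 patients are the allowance for loss and withdrawal of consent, not a forecast of antimalarial users. The exact 95% interval for 4/73 is 1.5% to 13.4%, so every scenario with k from 1 to 4 lies within sampling error. That limits the practical weight of the shift. It does not remove the point, because a sampling interval does not account for bias in one direction.

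**Conclusion.** The point holds in a limited form. The withdrawal rule and the censoring of withdrawals are in the text, and so is the absence of any check on the primary outcome. That the cure rate can be biased upward follows if returning illness prompts some of the drug use. The documents do not support saying that it is biased, because they give no frequency or reasons.

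Under the stated assumptions, with every hidden case a true failure, four such patients nearly double the failure rate, from about 5% to about 10%. That shift is about the size of the planned 5-point margin of error. It shrinks in proportion if only some were failing, and vanishes if outside drug use is unrelated to malaria. The 21.6% figure bounds total attrition and should not be read as an estimate of the effect of self-treatment. This is a worthwhile, low-cost improvement; it does not invalidate the design.

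**What to change.** 1. **Reconcile the withdrawal section with Annex 4, for outcome classification only.** State that a patient who reports outside antimalarial use, and whose slide at that contact meets an Annex 4 criterion, is analysed as a failure on that date and not censored.
2. **Add one prespecified sensitivity analysis to the Statistical Analysis section.** Keep both primary analyses and define the per-protocol population. In the added analysis, count every withdrawal after day 3 for antimalarial use as a failure on the date of use, whatever the slide shows. Leave censored any antibiotic use recorded as being for another illness. The rule should not be limited to patients without a negative slide. A smear is planned at every contact, and a recurrence cleared by the outside drug would be slide-negative, so such a rule would catch almost no one.
3. **Report withdrawals by reason,** and give the rate with all incomplete patients counted as failures, labelled as a bound on total attrition.

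The cost is a few sentences and extra rows of results. The smears are already planned, and the case record form already has rows for concomitant treatment and reasons for withdrawal. The reason for and date of the drug use must be noted there. Treatment and visits do not change. The downside is that the sensitivity rate will be less favourable. It may also count reinfections or presumptive treatment that could not be sampled for molecular correction, so it should stand beside the primary estimate and not replace it.
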